6.4 Study Intervention Adherence

The actual, measured temperature profile for each run will be automatically saved to Device memory, as will the time and date of each treatment run. These data will be accessible via a USB port that is covered by a hatch on the device body and will be downloaded by SNS. This data is an

independent record of the expected device performance and treatment adherence and will be used for confirmation purposes and planned analyses, not for confirming adherence in real time. Study participants will not be withdrawn by the study staff for significant treatment non-adherence.

7 Study Intervention Discontinuation and Participant Discontinuation/Withdrawal

7.1 Discontinuation of Study Intervention

All AEs will be evaluated by site personnel on an individual basis to determine whether the occurrence may be related to device use. Any issues related to safety concerns will promptly be referred to the site principal investigator, who can terminate the participant's further participation in the study if necessary.

Should a serious adverse event occur that is deemed to be likely related to device use, the potential for the universality will be assessed within 48 hours. If evidence suggests that treatments with the device could create a safety concern for participants, as deemed by the medical monitor, the study will be paused or stopped early, as appropriate.

It should be noted that the above scenario is considered to be highly unlikely. The device has been designated as NSR by the FDA, and there were no reports of serious or unexpected AEs that were potentially related to device in either the PD single-site RCT or the episodic migraine RCT.

7.2 Participant Discontinuation/Withdrawal from the Study

7.2.1 Withdrawal Criteria

Participants must be withdrawn from the clinical trial if any of the following events occur:

- the participant is significantly non-adherent to the requirements of the protocol (principal investigator & Sponsor decision),
- the participant develops an illness or condition that would interfere with his/her continued participation,
- the participant withdraws his/her consent,
- the participant's study partner withdraws his/her consent and no replacement can be found
- the principal investigator feels that it is the participant's best interest to be withdrawn,
- SNS discontinues the study or has achieved the targeted enrollment,

If the participant is discontinued from the participation in the study for any reason, the principal investigator must make every effort to perform all evaluations for the final visit, even virtually, if necessary, collect the device from the participant and document the reasons for discontinuation. If the participant withdraws from the study due to an adverse event that is potentially related to use of the device, the study staff should continue to follow up with the participant at regular intervals, and at least every two weeks until the AE resolves or until the participant withdraws consent for the follow-up procedure.

If a participant's study partner withdraws their consent from the study, a new study partner who meets the criteria [See Section 5.1] may be identified and consented to the study. If a suitable study partner cannot be found, the participant will be withdrawn from the study.

Participants that withdraw early will be excluded from the per protocol analysis.

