The results from the single-site RCT study provide strong evidence to support the safety and effectiveness of TNM™ Device treatments for managing the symptoms associated with PD. TNM™ Device treatments in this study utilized the same time-varying waveform and BID schedule as was used in a pivotal study that demonstrated TNM™ is a safe and effective

prophylactic for episodic migraine. The study described herein will utilize the same active treatment waveform and BID treatment regimen as were used in these previous studies.

In this study, participants will treat for 12 weeks (84 days) rather than 8 weeks (56 days), as was the case for the single-site RCT study. The selection of a longer treatment interval was based on the finding that the treatment response, including measures of NMS burden, did not reach an asymptote during the 8 weeks of treatment. These results suggest that additional gains may be obtained with longer treatment intervals. Notably, 12-week treatment intervals were shown to be safe for the indication of episodic migraine, and there has been no evidence from a small crossover study in PD that treatment intervals of 12-16 weeks of treatments increases the risk of device-related AEs relative to 8 weeks. The treatment interval in this study will be limited to 12 weeks to minimize confounding variables that may arise with participants changing concomitant medications.

The primary goal of this study is to replicate the results obtained from the PD single-site RCT in a multicenter RCT. As such, this study will focus on comparing an active treatment to a passive treatment.

4.4 End of Study Definition for RCT:

Participants will continue to be enrolled in the RCT until at least 184 participants have randomized. All other study participants that have been randomized into the RCT at this point will be allowed to continue in the RCT and enroll in and complete the OLE. The RCT will end when the final participant has completed the end of treatment assessment, at which point, the RCT will be closed out and analysis will occur.

4.5 End of Study Definition for OLE:

The end of study for the OLE will be considered complete when participants who have enrolled in the OLE are no longer being examined or the last participant's last study visit has occurred at week 52 (day 365 +/- 3 days) and or early termination has occurred.

5 Study population

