9.1 Sample Size Determination

The sample size for this study was set to achieve > 90% power to detect the minimal clinically important difference (MCID) of -2.64 points in the MDS-UPDRS: Part I⁶⁰. The estimated group sample sizes of 83 and 83 (166 total) to complete assumes a rate of attrition of 10% during the RCT and was set to achieve 89% power to detect a difference of -2.64 points in the MDS-UPDRS Part I total score between the null hypothesis that both group average change scores are equal and the alternative hypothesis that the average change score of the treatment group is -2.64 points less than that of the passive treatment group with estimated within group standard deviation of 5.32 points and with a 2-sided significance level (alpha) of 0.05. Competitive enrollment will close once 184 participants have been randomized into the RCT. This number allows for the maintenance of 89% power to detect the estimated MCID at the end of the RCT and at the end of the first treatment period in the OLE assuming 10% attrition during each of those two periods.

Note that the primary endpoint is the MDS-NMS, not the MDS-UPDRS: Part I. However, the two scales are highly correlated ($r_s=0.75$)¹, and the MDS-UPDRS: Part I has a pre-established MCID⁵⁹ whereas the MDS-NMS does not. The sample size (184 to randomize), derived from the MDS-UPDRS: Part I achieves >90% power to detect the estimated MCID of -35 points in the MDS-NMS. Participants will continue to be enrolled in the RCT until at least 184 participants have randomized, and if there are additional participant withdrawals, they will not be replaced. Participants who have entered the baseline period but have not yet randomized when the competitive enrollment target is achieved may be withdrawn from the study prior to randomization and, as a result, would not be included in any of the analyses. Data from all randomized study participants will be evaluated for analyses of safety and efficacy.

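### The mandatory withdrawal list in Protocol 7.2.1 conflicts in part with 6.4 on non-adherence and directly with 4.4 and 9.1 on reaching the enrolment target, so the follow-up of randomised participants is not clearly protected

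*Protocol*

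**What the plan says.** Protocol 7.2.1 opens in mandatory terms: "Participants must be withdrawn from the clinical trial if any of the following events occur". Two of its items matter here.

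- **Non-adherence:** "the participant is significantly non-adherent to the requirements of the protocol (principal investigator & Sponsor decision").
- **Enrolment:** "SNS discontinues the study or has achieved the targeted enrollment". The item is not limited to people who have not yet been randomised.

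Other sections say something different.

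- **Protocol 6.4:** "Study participants will not be withdrawn by the study staff for significant treatment non-adherence".
- **Protocol 4.4**, on what happens once 184 are randomised: "All other study participants that have been randomized into the RCT at this point will be allowed to continue in the RCT".
- **Protocol 9.1:** people in the baseline period when the target is met "may be withdrawn from the study prior to randomization". RCT SAP section 4 says the same.
- **RCT SAP 7.2:** the ITT population, used for the primary analysis, is everyone randomised. Adherence of at least 70% is a condition for the per-protocol set only.
- **RCT SAP 7.7 and 7.10.2:** the primary model is an MMRM, described as unbiased when data are missing at random. Missing data are expected to be unrelated to arm.

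On leaving the study, 7.2.1 adds that "the principal investigator must make every effort to perform all evaluations for the final visit, even virtually, if necessary". It requires continued follow-up afterwards only for adverse events potentially related to the device.

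**The concern.** Twice-daily treatment is the central requirement of this protocol. A participant who largely stops using the device therefore appears to meet the 7.2.1 trigger, although 6.4 says that study staff will not withdraw such a person. Under-use will be known during the trial: section 4.1.1 has staff review device adherence at the two-weekly calls.

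What is at stake is the ITT estimate. People may under-use the device because they see no benefit or find it uncomfortable. Only the active arm receives powered thermal stimulation, so these reasons may differ by arm. If under-use leads to withdrawal, whether the day 113 MDS-NMS is observed may depend on treatment experience. That would strain the missing-at-random assumption. Only RCT completers may enter the OLE (OLE SAP section 2), so each such withdrawal from the passive arm also reduces the OLE passive-active comparison.

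The enrolment item is a different kind of problem. Read literally, it would end participation for people still on treatment when the 184th participant is randomised. That would shorten follow-up, but for a reason that has nothing to do with how anyone is responding.

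**Working it through.** **1. The passages side by side**

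| Topic | Protocol 7.2.1 | Elsewhere | Relation |
|---|---|---|---|
| Non-adherence | Mandatory withdrawal; covers protocol requirements; decided by principal investigator and Sponsor | 6.4: no withdrawal; covers treatment; refers to study staff | Partial conflict: actor and scope differ, but 7.2.1 has no exception for treatment |
| Adherence in the analysis | Under-users leave the trial | RCT SAP 7.2: 70% threshold defines the per-protocol set; ITT keeps all randomised | Threshold presupposes that under-users are retained |
| Target reached | Mandatory withdrawal, no limit on whom | 4.4: randomised participants continue. 9.1 and RCT SAP section 4: only those not yet randomised, and optional | Direct conflict |

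No other section reconciles these.

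**2. The plan's own power figure**

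Inputs (Protocol 9.1, RCT SAP section 4): difference 2.64 points on MDS-UPDRS Part I, SD 5.32, two-sided alpha 0.05, 83 completers per arm.

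- Noncentrality = 2.64 / (5.32 × √(2/83)) = 3.197.
- Normal approximation: Φ(3.197 − 1.960) = 89.2%, which matches the RCT SAP.
- Noncentral t with 164 df: 88.8%.
- Attrition: 184 × 0.90 = 165.6, about 166, as stated.

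**3. Power if more participants are withdrawn**

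The documents give no rate for such withdrawals. A further 5% is an assumption. Taken from those randomised, 184 × 0.85 / 2 = 78.2 per arm; taken from completers, 83 × 0.95 = 78.9.

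| Per arm | Two-sided 0.05 (sizing basis) | One-sided 0.05 (primary test, RCT SAP 7.7.1.1) |
|---|---|---|
| 83 | 88.8% | 93.8% |
| 79 | 87.3% | 92.8% |
| 78 | 86.9% | 92.5% |

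Over a wider assumed range of total attrition (two-sided, normal approximation), power is 89.1% at 10%, 87.4% at 15%, 85.3% at 20%, 83.0% at 25% and 80.4% at 30%.

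**4. Illustration of bias**

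Assume that a share w of the active arm is withdrawn for under-use with no benefit, that the passive arm is unaffected, and that the true ITT difference is 2.64. An estimate from the remaining participants would be 2.64 / (1 − w).

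| w | Estimate | Overstatement |
|---|---|---|
| 5% | 2.78 | 0.14 |
| 10% | 2.93 | 0.29 |
| 15% | 3.11 | 0.47 |

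This is a completer-type calculation. The MMRM also uses earlier visits and could be less affected.

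**The case against.** The strongest reply is that 6.4 and 7.2.1 can be read together. Section 6.4 concerns use of the device and binds study staff. Section 7.2.1 concerns protocol requirements in general, such as missed visits, and reserves the decision to the principal investigator and Sponsor. Sponsor involvement is a common check across sites. Section 6.4 also says that device logs are not for confirming adherence in real time. This reading is fair, and it is why the conflict is partial. It does not close the gap: 7.2.1 makes no exception for treatment, and an investigator and Sponsor decision would still end participation for the behaviour that 6.4 protects.

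A reader might infer that a withdrawn participant's outcome is simply lost. The documents do not support that. Section 7.2.1 requires every effort to complete the final-visit evaluations, section 4.1.1 provides for an early-termination visit that includes the MDS-NMS, and MDS-NMS data from days 57 and 85 enter the MMRM. RCT SAP 7.10.8 adds completer and best-responder comparisons. What remains is narrower. An early visit may fall well before day 113. RCT SAP 7.7.1 defines the primary endpoint at day 113 and does not say how early-termination data enter the model, whereas 7.8.2 does count early-withdrawal data for the mini-BESTest. No missing-not-at-random model is named for the primary endpoint.

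A reader might also infer that both conflicts cut follow-up short for reasons tied to outcome. That holds at most for the non-adherence item. The enrolment item is administrative, and sites are unlikely to apply it literally given 4.4.

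**Conclusion.** The inconsistencies are real and stand in the current text. The enrolment conflict is direct but is a matter of wording with little practical risk. The non-adherence conflict is partial and has the more serious potential consequence, because it could tie missing primary data to treatment experience.

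The effect on power is small. With an assumed further 5% withdrawn, two-sided power on Part I falls by 1.5 to 1.9 percentage points, from 88.8% to about 87%; on the one-sided basis of the primary test it stays above 92%. Bias is the main concern, and its size cannot be derived from the documents. The overstatement of 0.14 to 0.47 points rests on assumed withdrawal in one arm only, zero benefit in those withdrawn and a completer-type estimate.

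The documents do not show that such withdrawals will be frequent or will differ by arm. Which withdrawal rule should apply is not judged here. This should be corrected, but it does not by itself undermine the primary analysis.

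**What to change.** 1. Reconcile 7.2.1 with 6.4 on non-adherence so that one rule applies at all sites. The choice of rule belongs to the sponsor and investigators.
2. Bring the enrolment item in 7.2.1 into line with what 4.4, 9.1 and RCT SAP section 4 already state, by limiting it to participants not yet randomised.
3. Separate under-use or stopping of the device from withdrawal from outcome collection. The assessments already scheduled through day 113 would then be sought from randomised participants who under-use or stop the device, where they still consent and no other 7.2.1 criterion applies. The illness, study-partner and best-interest criteria are left as they are.

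The cost is an amendment of protocol wording. The visits are already in the schedule of events, so no new assessments are needed, only the effort of collecting them from people who have stopped or reduced treatment.

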7.2.2 Lost to Follow-Up

If a participant misses a visit, the study staff should call the participant/study partner within 24 hours to reschedule, and the visit should be rescheduled for as soon as possible after the missed appointment and within 5 business days. The reason for rescheduling should be noted. If there is no response from the participant or their study partner the study staff will continue to contact the participant/study partner daily for 1 week or until contact is made, then weekly for 3 weeks. If the prior steps are unsuccessful, a certified letter should be sent to the participant requesting they contact the study staff immediately. The participant is considered lost to follow-up if all the prior steps are performed with no contact made. Documentation of all phone calls, and copies of all correspondence should be maintained in the participant's source documentation.

8 Safety Oversight

8.1 Device Deficiency

A device deficiency is an inadequacy of a medical device related to its identity, quality, durability, reliability, safety, or performance, such as malfunction, misuse or use error and inadequate labeling.

All device deficiencies will be documented, and the device will be returned to the device manufacturer for analysis, if possible. Device deficiencies are NOT to be reported as AEs. However, if there is an AE that results from a device deficiency, that specific event would be recorded on the appropriate CRF.

8.2 Adverse Events (AEs), Adverse Device Effects (ADEs), Serious AEs (SAEs), Serious Adverse Device Effects (SADEs), Unanticipated Adverse Device Effects (UADE) and Unanticipated Problem Reporting

8.2.1 AEs, ADEs, SAEs, SADEs and UADEs will be defined per ISO14155:2020 and/or 21 CFR Part 812, as described below.8.2.1 Adverse Event (AE):

An AE is any untoward medical occurrence, unintended disease or injury, or untoward clinical signs (including abnormal laboratory findings) in participants, users, or other persons, whether or not related to the investigational medical device. This definition includes events related to the investigational medical device and the events related to the procedures involved. For users and other persons, this definition is restricted to events related to the investigational device. AEs will be collected starting from the time the participant signs informed consent until the follow-up period is completed.

8.2.2 Adverse Device Effect (ADE):

An Adverse Device Effect (ADE) is an AE related to the use of an investigational medical device. This definition includes AEs resulting from insufficient or inadequate instructions for use, deployment, implantation, installation, or operation, or any malfunction of the investigational medical device. This definition includes any event resulting from use error or from intentional misuse of the investigational medical device.

Traditional, diagnostic CVS has been used for roughly a century, and there are no reports in literature of significant adverse events.

Therapeutic CVS has been studied for use in prevention of episodic migraine and in treatment of symptoms of Parkinson’s Disease. Results of these studies (including one multisite RCT and one single-site RCT, respectively), resulted in neither serious nor unanticipated/unexpected adverse events related to the study device. Additionally, there was no reduction in balance and no negative change in either mood or cognition.

The following AEs are known, possible side effects of using the investigational device:

More likely:

- Dizziness (whirling or spinning sensation; may also be called “giddiness” or vertigo)
- Drowsiness
- Treatment site discomfort (skin itching, skin irritation felt within the ear canal or around the ear area or pressure felt within ear canal)

Less likely:

- Nausea
- Vomiting
- Headache
- Tinnitus

All of the potential AEs noted above are expected to resolve soon after use of the investigational Device is stopped.

8.2.3 Serious Adverse Event (SAE):

A Serious Adverse Event (SAE) is an AE that has

- Led to death,
- Led to serious deterioration in the health of the participant, that either resulted in
 1. A life-threatening illness or injury, or
 2. A permanent impairment of a body structure or a body function, or
 3. In-patient or prolonged hospitalization, or
 4. Medical or surgical intervention to prevent life-threatening illness or injury or permanent impairment to a body structure or a body function,
- Led to fetal distress, fetal death or a congenital abnormality or birth defect

8.2.4 Serious Adverse Device Effect (SADE):

Adverse device effect that has resulted in any of the consequences characteristic of a serious adverse event.

8.2.5 Unanticipated Adverse Device Effect (UADE):

An Unanticipated Adverse Device Effect is a *serious* adverse effect on health or safety or any life-threatening problem or death caused by, or associated with, a device, if that effect,

problem, or death was not previously identified in nature, severity, or degree of incidence in the investigational plan or application (including a supplementary plan or application), or any other unanticipated serious problem associated with a device that relates to the rights, safety, or welfare of participants.

8.2.6 Procedures for AEs:

8.2.6.1 Documentation and assessment

- Following the informed consent process, clinical study participants will be routinely questioned about AEs at all visits from the clinical research staff. All AEs, regardless of treatment group or suspected causal relationship to the investigational device, will be recorded in the participants' source documentation.
- For all AEs, sufficient information will be obtained as to 1) determine the severity of the event; 2) assess the casual relationship between the adverse event and the investigational device; and 3) determine the outcome of the event.
- AEs will be followed until the event (or its sequelae) resolves or stabilizes at a level acceptable to the investigator and sponsor.

8.2.6.2 Causality and severity assessment

- The investigator will promptly review documented AEs to determine 1) if there is a reasonable possibility that the adverse event was caused by the investigational device or other study treatments and 2) if the adverse event meets the criteria for “*serious*.”
- If the investigator's final determination of causality is “possible or probable relationship to the investigational device or other study treatments,” the adverse effect will be classified as *associated with the use of the investigational device or other study treatments* for reporting purposes. If the investigator's final determination of causality is “*not related* to the investigational device or other study treatments,” this determination and the rationale for the determination will be documented.

8.2.6.3 Investigator Reporting AEs to the Sponsor and responsible IRB/REC

Reporting to the Sponsor:

- Adverse events will be submitted to the Sponsor.
- All serious and/or unanticipated adverse events will be submitted to the Sponsor as soon as possible, but no later than 10 days after the Investigator's first knowledge of the event.
- All serious and/or unanticipated/unexpected adverse events that involve a death must be reported within 24 hours of discovery.

Reporting to the IRB / REC:

- U.S. Investigators are additionally required to submit to their IRB a report of Unanticipated Adverse Device Effect (UADE) as soon as possible, but in no event later than 10 working days after the investigator first learns of the event (21 CFR 812.150(a)(1)). However, if the UADE involves a death, it must be reported within **24**

hours of discovery.

- U.K. Investigators are additionally required to submit to their REC all reports of UADEs within 15 days of the chief investigator becoming aware of the event.

UADEs will require unblinding but written permission must first be obtained from the study sponsor.

